10.4.2	Contraception Guidance	47
10.5	Appendix 5: Physician Global Assessment of Target Lesion	48

[REDACTED]	[REDACTED]

11	References.....	55
----	-----------------	----

List of Tables

Table 1:	Study Intervention(s) Administered	22
Table 2:	Study Arm(s)	22
Table 3:	Fitzpatrick Skin Type Scale.....	27
Table 4:	Criteria for Determining the Grade/Severity of Adverse Event Terms Not Specified by the National Cancer Institute CTCAE	42

List of Abbreviations

Term	Description
AE	adverse event
BSA	body surface area
CFR	Code of Federal Regulations
CONSORT	Consolidated Standards of Reporting Trials
COVID-19	coronavirus disease 2019
CTCAE	Common Terminology Criteria for Adverse Events
CV	cardiovascular
[REDACTED]	[REDACTED]
eCRF	electronic case report form
CRF	case report form
EDC	electronic data capture
FDA	Food and Drug Administration
FSH	follicle-stimulating hormone
GCP	Good Clinical Practice
HRT	hormonal replacement therapy
IB	Investigator's brochure
ICF	informed consent form
ICH	International Council for Harmonisation
IEC	independent ethics committee
IND	Investigational New Drug application
IRB	institutional review board
ITT	intent-to-treat
IU	international units
[REDACTED]	[REDACTED]
OC	observed case
[REDACTED]	[REDACTED]
PGA	Physician Global Assessment
[REDACTED]	[REDACTED]
PSO	psoriasis
QD	once daily
SAE	serious adverse event
SoA	schedule of activities
SD	standard deviation
SUSAR	suspected unexpected serious adverse reaction
TEAE	treatment-emergent adverse event
USA	United States of America
USPI	United States Prescribing Information
UV	ultraviolet
WOCBP	woman of childbearing potential
WONCBP	woman of nonchildbearing potential

1 Protocol Summary

1.1 Synopsis

Protocol Title: A Phase 4, open-label study to investigate the efficacy and safety of VTAMA® (tapinarof) cream, 1% in the treatment of plaque psoriasis occurring in the head and neck region

Brief Title: A study to investigate efficacy and safety of VTAMA® (tapinarof) cream, 1% in plaque psoriasis in the head and neck region

Regulatory Agency Identifier Number(s):

IND	104601
-----	--------

Rationale:

Plaque PSO in the head and neck region occurs commonly and is often underdiagnosed ([Merola 2016](#)). Scalp involvement occurs in 45% to 56% of individuals with PSO and facial PSO typically presents at a younger age and is estimated to affect nearly 50% of patients with PSO ([Bagel 2018](#); [Merola 2018](#)). The majority of patients with facial PSO also have scalp involvement ([Dopystalska 2018](#)). Scalp PSO can cause patients to feel embarrassed and self-conscious. Facial PSO can be even more devastating because it cannot be hidden with clothing. Despite the small surface area affected, disease in this area can result in considerable psychosocial challenges that are not captured by traditional scoring systems.

Topical corticosteroids are often used to treat plaque PSO in the head and neck region; however, due to the safety profile their use is limited to only short-term therapy. Other topical therapies such as vitamin D analogs offer better safety profiles, but with moderate efficacy. The use of any topical treatment in this area presents challenges because application may be burdensome or cosmetically unacceptable ([Mosca 2021](#)). Because many commonly used topical agents are not embraced by patients for use in this area due to lack of tolerability and cosmetic acceptability, lack of adherence is an issue that compounds the lack of efficacy and poor safety profiles associated with these therapies. Systemic treatment, such as biologics and oral therapy, is reserved for the more severe and resistant cases due to the more severe adverse effects and cost associated with these agents ([Beck 2018](#)). Dermavant has developed an effective, steroid-free, locally acting, cosmetically elegant topical therapy that is safe and tolerable and offers patients the opportunity for a treatment-free remittive period. Application of the product to plaque PSO in the head and neck region was permitted in the Phase 3 registrational trials to assess tolerability, but efficacy was not specifically evaluated in this region.

VTAMA (tapinarof) cream, 1% was approved by the FDA in May 2022 for the treatment of plaque PSO in adults. Tolerability in sensitive areas was excellent in Phase 3 pivotal studies and the long-term extension study for a total duration of up to 52 weeks ([Lebwohl 2021](#); data on file). This study will further assess efficacy and safety of VTAMA (tapinarof) cream, 1% when used to treat head and neck PSO.

Objectives and Endpoints:

Objectives	Endpoints
Primary	

 To evaluate the efficacy of VTAMA (tapinarof) cream, 1% in adults with plaque PSO in the head and neck region 	
 Percentage of participants who achieve a PGA (target lesion) score of clear (0) or almost clear (1) with a ≥ 2-grade improvement from Baseline at Week 12
Secondary	

 To assess onset of effect of VTAMA (tapinarof) cream, 1% in adults with plaque PSO in the head and neck region 	
 Time to achieve a PGA (target lesion) score of 0 or 1 with a ≥ 2-grade improvement from Baseline

 [REDACTED] 	
 [REDACTED]

Overall Design Synopsis:

Brief Summary:

The purpose of this open-label study is to evaluate the efficacy and safety of tapinarof cream, 1% in adults with plaque PSO occurring in the head and neck region. A target plaque PSO lesion in the head and neck region will be identified at Baseline, and efficacy of tapinarof will be assessed with a PGA evaluation.

[REDACTED] Safety and tolerability will be assessed by evaluation of AEs [REDACTED]

VTAMA will be dispensed and will be administered at home between clinic visits as instructed by site personnel. Application instructions will be reviewed at all clinic visits during the study, except during the final treatment/end-of-study visits. Participants will be instructed to apply cream QD to all affected areas on the head and neck, including the target lesion. Cream should be applied to newly appearing areas on the head and neck as well as areas in this region that improve or clear during the study. Participants may apply cream to any other lesions on the body although efficacy will only be assessed at the target lesion (PGA) [REDACTED]. Participants will apply sufficient cream to cover completely each lesion with a thin layer of medication and will record the time of application in a daily diary provided by the study site. Participants will be instructed to maintain the approximate dosing time chosen at the beginning of the study for their full study participation.

Number of Participants:

Approximately 30 participants will be enrolled.

Note: Enrolled means participants agreement to participate in a clinical study following completion of the informed consent process and screening. Potential participants who are screened for the purpose of determining eligibility for the study, but do not participate in the study, are not considered enrolled, unless otherwise specified by the protocol. A participant will be considered enrolled if the informed consent is not withdrawn prior to participating in any study activity after screening.

Study Arms and Duration:

VTAMA (tapinarof) cream, 1% is a white to off-white cream containing 1% weight/weight (10 mg/g) tapinarof, supplied in 60-gram tubes. VTAMA is to be administered by the participant QD via topical application of a thin layer to affected areas in accordance with instructions in the USPI.

Dosing may be interrupted if deemed necessary by the Investigator for management of AEs.

Study duration:

- The study duration will be up to 17 weeks.
- The treatment duration will be up to 12 weeks.
- The follow-up period will be up to 1 week.

Statistical Methods

Efficacy, safety, [REDACTED] [REDACTED] [REDACTED] [REDACTED] will be summarized for the ITT population.

Every effort will be made to collect complete data at all visits. All efficacy data will be summarized based on OCs. The primary and exploratory efficacy endpoints will also be summarized utilizing the last observation

carried forward method to impute missing data [REDACTED] [REDACTED]
[REDACTED]

Efficacy and Safety Analyses

Demographics and baseline characteristics, efficacy, and all safety assessments [REDACTED] [REDACTED] will be summarized descriptively, no statistical comparisons will be performed. Continuous data will be summarized by number of participants, mean, SD, median, minimum, and maximum, and categorical data will be summarized by frequency counts and percentages. The 95% confidence intervals will be reported as appropriate. Median time to event analyses will use the Kaplan-Meier product limit method (if estimable).

[figure not shown]
Determination of Sample Size

The sample size for this study is based on clinical considerations only. No formal sample size calculation will be performed. A total of 30 participants is planned for this study which is considered adequate to evaluate the efficacy and safety for the treatment of plaque PSO occurring in the head and neck region.

[figure not shown]
Data Monitoring/Other Committee:

No data monitoring committee has been appointed for this study.

1.2 Schema

1.3 Schedule of Activities

2 Introduction

VTAMA (tapinarof) cream, 1% was approved by the FDA in May 2022 for the treatment of plaque PSO in adults. Tolerability in sensitive areas, including the face, was excellent in Phase 3 pivotal studies and the long-term extension study for a total duration of up to 52 weeks ([Lebwohl](#) 2021; data on file).

2.1 Study Rationale

This study will further assess efficacy and safety of VTAMA (tapinarof) cream, 1% when used to treat PSO in the head and neck region.

2.2 Background

Occurrence in the head and neck region is common among patients with plaque PSO. Scalp involvement occurs in 45% to 56% of individuals with PSO, and facial PSO typically presents at a younger age and is estimated to affect nearly 50% of patients with PSO ([Bagel](#) 2018; [Merola](#) 2018). The majority of patients with facial PSO also have scalp involvement ([Dopytalska](#) 2018). Scalp PSO can cause patients to feel embarrassed and self-conscious. Facial PSO can be even more devastating because it cannot be hidden with clothing. Despite the small surface area affected, disease in this area can result in considerable psychosocial challenges that are not captured by traditional scoring systems.

Topical corticosteroids are often used to treat plaque PSO in the head and neck region; however, due to the safety profile, their use is limited to only short-term therapy. Other topical therapies such as vitamin D analogs offer better safety profiles but with moderate efficacy. The use of any topical treatment in this area presents challenges because application may be burdensome or cosmetically unacceptable ([Mosca](#) 2021).

Because many commonly used topical agents are not embraced by patients for use in this area due to lack of tolerability and cosmetic acceptability, lack of adherence is an issue that compounds the lack of efficacy and poor safety profiles associated with these therapies. Systemic treatment, such as biologics and oral therapy, is reserved for the more severe and resistant cases due to the more severe adverse effects associated with systemic treatment ([Beck](#) 2018). There is a clear medical need for an effective, steroid-free, locally acting topical therapy that is safe and tolerable and offers patients the opportunity for a treatment-free remittive period given the challenges of treating this area.

VTAMA (tapinarof) cream, 1% is a novel, cosmetically elegant, steroid-free topical cream that has demonstrated clinically meaningful and highly statistically significant efficacy in the treatment of plaque PSO and, thus, has the potential to meet the need in patients with plaque PSO in the head and neck region.

Application of the product to plaque PSO in the head and neck region was permitted in the Phase 3 registrational trials to assess tolerability. In addition, efficacy assessments in registrational trials included evaluation of plaques located in the head and neck region as part of the overall response in treated areas. Although efficacy in the treatment of scalp PSO was not evaluated, the USPI does not restrict application of VTAMA to the scalp. A detailed description of the chemistry, pharmacology, efficacy, and safety of VTAMA (tapinarof) cream, 1% is provided in the IB.

2.3 Benefit/Risk Assessment

More detailed information about the known and expected benefits and risks and reasonably expected AEs of VTAMA (tapinarof) cream, 1% may be found in the IB.

2.3.1 Risk Assessment

No major safety concerns were identified during the development program; no deaths or SAEs were considered related to VTAMA (tapinarof) cream, 1%. Most AEs were mild localized skin reactions of a type commonly observed and managed by dermatologists. A low incidence of safety issues, serious or non-serious, were observed. The common AEs associated with the administration of VTAMA (tapinarof) cream, 1% in the clinical trials for plaque PSO were folliculitis, contact dermatitis, and headache. Folliculitis events were generally mild and well tolerated and did not worsen or progress over time with continued treatment. The vast majority of participants elected to continue with VTAMA (tapinarof) cream, 1%, suggesting the perceived benefit outweighs the burden of folliculitis. See Section [10.3.5](#) for further information on the management of follicular events. Observations suggest that the events of contact dermatitis experienced by participants with plaque PSO may not represent allergic contact dermatitis.

2.3.2 Benefit Assessment

VTAMA (tapinarof) cream is a novel, cosmetically elegant, steroid-free topical cream that has demonstrated clinically meaningful and highly statistically significant efficacy in the treatment of plaque PSO consistently across the clinical program. Benefits to participants include rapid improvement in signs and symptoms that persists with continued use, the ability to achieve complete disease clearance, and maintenance of disease control via a remittive effect after treatment discontinuation in a convenient once-daily topical therapy that can be administered for extended treatment durations with no limit to the size or location of the treatment area. The remittive effect off therapy observed for VTAMA (tapinarof) cream, 1% is a unique and differentiating attribute that, along with durability on therapy, provides patients with a new option for long-term disease management. These attributes are coupled with minimal systemic absorption and a favorable safety and tolerability profile.

2.3.3 Overall Benefit Risk Conclusion

Given the measures taken to minimize risk to participants participating in this study, the potential risks identified in association with VTAMA (tapinarof) cream are justified by the anticipated benefits that may be afforded to participants with plaque PSO in the head and neck region. Please see USPI for the most up-to-date information.

3 Objectives and Endpoints

Objectives	Endpoints
Primary	

 • To evaluate the efficacy of VTAMA (tapinarof) cream, 1% in adults with plaque PSO in the head and neck region 	
 • Percentage of participants who achieve a PGA (target lesion) score of clear (0) or almost clear (1) with a ≥ 2-grade improvement from Baseline at Week 12
Secondary	

 • To assess onset of effect of VTAMA (tapinarof) cream, 1% in adults with plaque PSO in the head and neck region 	
 • Time to achieve a PGA (target lesion) score of 0 or 1 with a ≥ 2-grade improvement from Baseline

 • [REDACTED] 	
 • [REDACTED]

4 Study Design

4.1 Overall Design

This is a single-group, open-label, multicenter study to evaluate the safety and efficacy of VTAMA (tapinarof) cream, 1% in the treatment of plaque PSO in the head and neck region. Participants will treat plaque PSO in the head and neck region with VTAMA (tapinarof) cream, 1% QD for 12 weeks. Efficacy of the treatment of plaque PSO in the head and neck region will be assessed with a PGA evaluation of a target lesion selected as representative of the participant's disease in the head and neck region. [REDACTED]

[REDACTED] Participants will be allowed to treat plaque PSO in other body areas according to instructions provided in the USPI, but no assessments of efficacy will be performed outside of the head and neck region. Safety and tolerability will be assessed by evaluation of AEs [REDACTED]

Study duration:

- The study duration will be up to 17 weeks.
- The treatment duration will be up to 12 weeks.
- The follow-up period will be up to 1 week.

4.2 Scientific Rationale for Study Design

The safety and efficacy of VTAMA (tapinarof) cream, 1% in the treatment of plaque PSO were established in Phase 3 studies, which included the treatment of sensitive areas. This study is intended to broaden the understanding of the safety and efficacy of VTAMA (tapinarof) cream, 1% in the treatment of plaque PSO occurring in the head and neck region. Efficacy and tolerability in this area will also be assessed.

The PGA is a clinical tool for assessing the current state/severity of a participant's PSO at a given time point. It is a static 5-point morphological assessment of overall disease severity, as determined by the Investigator, using the clinical characteristics of erythema, scaling, and plaque thickness/elevation as guidelines; higher PGA scores represent more severe disease. Improvements in PGA generally correlate with improvements in quality of life. A target plaque PSO lesion in the head and neck region will be identified at Baseline and efficacy of tapinarof will be assessed with a PGA evaluation. The primary endpoint will assess the percentage of participants who achieve a PGA (target lesion) score of clear (0) or almost clear (1) with a ≥ 2 -grade improvement from Baseline at Week 12. This type of endpoint is well established as a means of measuring the success of treatments in plaque PSO. The secondary endpoint will assess the time to achieve a PGA (target lesion) score of 0 or 1, as onset of action is incredibly important to patients in the clinic. [REDACTED]

[REDACTED]

4.3 Justification for Dose

The FDA-approved dosing regimen for VTAMA (tapinarof) cream, 1% for the treatment of plaque PSO is QD dosing and will be followed in this study. This regimen is based on the evaluation of various tapinarof regimens in participants with plaque PSO and atopic dermatitis and the success of this regimen in Phase 3 studies in participants with plaque PSO.

4.4 End-of-Study Definition

The end of the study is defined as the date of the last visit of the last participant in the study.

5 Study Population

Prospective approval of protocol deviations to recruitment and enrollment criteria, also known as protocol waivers or exemptions, is not permitted.

5.1 Inclusion Criteria

Participants are eligible to be included in the study only if all of the following criteria apply:

Age

1. Participant must be 18 years of age or older, at the time of signing the informed consent.

Type of Participant and Disease Characteristics

2. Participants with clinical diagnosis of plaque PSO, including lesion(s) in the head and neck region and stable disease in the head and neck region for at least 3 months prior to the study
3. Participant has a plaque PSO lesion in the head and neck region that is suitable for evaluation as the target lesion and has a PGA (target lesion) score of 2 (mild), 3 (moderate), or 4 (severe) at Screening and Baseline.

Sex and Contraceptive/Barrier Requirements

Contraceptive use by men and women should be consistent with local regulations regarding the methods of contraception for those participating in clinical studies.

4. Female participants:

A female participant is eligible to participate if she is not pregnant or breastfeeding, and one of the following conditions applies:

- Is a WONCBP as defined in [Appendix 4](#) Contraceptive and Barrier Guidance
OR
- Is a WOCBP and using an acceptable contraceptive method as described in [Appendix 4](#) Contraceptive and Barrier Guidance during the treatment period, until after the last dose of study product. The Investigator should evaluate the potential for contraceptive method failure (e.g., noncompliance, recently initiated) in relationship to the first dose of study product.
 - A WOCBP must have a negative urine pregnancy test before the first dose of study product, see Section [8.3.1](#) Pregnancy Testing.
 - The Investigator is responsible for review of medical history, menstrual history, and recent sexual activity to decrease the risk for inclusion of a woman with an early undetected pregnancy.

Informed Consent

5. Capable of giving signed informed consent as described in [Appendix 1](#) which includes compliance with the requirements and restrictions listed in the ICF and in this protocol; written informed consent must be obtained prior to any study-related procedures.

5.2 Exclusion Criteria

Participants are excluded from the study if any of the following criteria apply:

Medical Conditions

1. Diagnosis of a type of psoriasis other than plaque PSO
2. Any sign of infection of any of the psoriatic lesions
3. Concurrent significant dermatologic or inflammatory condition other than plaque PSO that, in the Investigator's opinion, would make it difficult to interpret data or assessments during the study
4. A history of or ongoing serious illness or medical, physical, or psychiatric condition(s) that, in the Investigator's opinion, may interfere with participation in the study and ability to understand and give informed consent
5. History of sensitivity to the study product, or components thereof, or a history of drug or other allergy that, in the opinion of the Investigator or Medical Monitor, contraindicates participation in the study

Prior/Concomitant Therapy

6. Previous OR current use of VTAMA
7. Use of any prohibited medication within the indicated period before the Baseline visit

NOTE: Prohibited concomitant medications, therapy, etc., during the defined period are as listed in the bullets below. If a participant requires any of these medications throughout the study period, he/she may be excluded from or discontinued from the study.

- Minimum of 5 half-lives for biologic agents: e.g., 12 months for rituximab; 8 months for ustekinumab; 5 months for secukinumab, risankizumab, or tildrakizumab; 12 weeks for golimumab or guselkumab; 10 weeks for ixekizumab or infliximab; 8 weeks for infliximab, adalimumab, alefacept, or brodalumab; and 4 weeks for etanercept
- Four weeks for systemic treatments: deucravacitinib, cyclosporin, interferon, methotrexate, apremilast, tofacitinib, mycophenolate, thioguanine, hydroxyurea, sirolimus, azathioprine, other systemic immunosuppressive or immunomodulating agents, fumaric acid derivatives, vitamin D3 and analogs (> 5000 IU / day), retinoids (e.g., acitretin, isotretinoin), psolarens, corticosteroids, or adrenocorticotropic hormone analogs
- Two weeks for immunizations with a live viral component; drugs known to possibly worsen PSO, such as beta-blockers (e.g., propranolol), lithium, iodides, angiotensin-converting enzyme inhibitors, and indomethacin, unless on a stable dose for > 12 weeks
- One week for medicated shampoos containing corticosteroids, vitamin D analogs, salicylic acid, or coal tar and 2 weeks for topical minoxidil
- With the exception of non-medicated emollients, 2 weeks for topical treatments including corticosteroids, roflumilast, antihistamines, immunomodulators, anthralin (dithranol), vitamin D derivatives (e.g., calcipotriene, calcipotriol), retinoids (Note: 4 weeks for tazarotene), or coal tar

NOTE: If participants are on a stable regimen of non-medicated emollient(s), they may continue to use the same emollient(s) on nonlesional skin during the study.

Prior/Concurrent Clinical Study Experience

8. Current enrollment OR past participation in another investigational study in which tapinarof was administered
9. The participant has received an investigational product within the following time period prior to the first dosing day in the current study: 30 days, 5 half-lives, or twice the duration of the biological effect of the study product (whichever is longer).

Other Exclusion Criteria

10. UV light therapy or prolonged exposure to natural or artificial sources of UV radiation (e.g., phototherapy, tanning beds/booths, or therapeutic sunbathing) within 4 weeks prior to the Baseline visit and/or plans to have such exposures during the study which could potentially impact the participant's PSO (as determined by the Investigator).

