6.9 Prior and Concomitant Therapy

Any medication or vaccine, including over the counter or prescription medicines, recreational drugs, vitamins, and/or herbal supplements, as well as non-medicated emollients, that the participant is utilizing at the time of consent or receives during the study must be recorded along with:

- Reason for use
- Dates of administration including start and end dates
- Dosage information including dose and frequency

The medical monitor should be contacted if there are any questions regarding concomitant or prior therapy.

Concomitant medications for medical treatment of other conditions are allowed, under the condition that the dosage and administration of these treatments are not planned to change from the Baseline visit to the completion of the study or discontinuation, and that the medication is not a prohibited medication as described in Section 5.2.

In the event of skin infection, topical antibacterial agents can be applied to the infected area; however, study product must not be applied to the area until the skin infection is healed.

Participants may use non-medicated shampoos (must not contain corticosteroids, vitamin D analogs, salicylic acid, or coal tar). If participants are on a stable regimen of non-medicated emollient(s), they may continue to use the same emollient(s) on nonlesional skin during the study. The same emollient should be used throughout participation in the study.

7 Discontinuation of Study Intervention and Participant Discontinuation/Withdrawal

Discontinuation of specific sites or of the study as a whole are detailed in [Appendix 1](#).

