7.1.1 Temporary Interruption

Some dermatological reactions have been observed following treatment with VTAMA (tapinarof) cream, 1% (see Section [2.3.1](#)). After cessation of exposure, dermatological reactions generally subside spontaneously or with topical treatments.

In this study, treatment of plaque PSO in the head and neck region with study product may be temporarily interrupted for dermatological reactions. If treatment is interrupted due to a safety issue, the Medical Monitor will be contacted, and the event documented in the eCRF.

See Section [10.3.5](#) for further information on the management of follicular events.

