7.2 Participant Discontinuation/Withdrawal from the Study

- A participant may withdraw from the study at any time at the participant's own request for any reason (or without providing any reason).
- A participant may be withdrawn at any time at the discretion of the Investigator for safety or compliance reasons.
- At the time of discontinuing from the study, if possible, an early discontinuation visit should be conducted, as shown in the SoA. See SoA for data to be collected at the time of study discontinuation and follow-up and for any further evaluations that need to be completed.
- The participant will be permanently discontinued from the study product and the study at that time.
- If the participant withdraws consent for disclosure of future information, the Sponsor may retain and continue to use any data collected before such a withdrawal of consent.
- If a participant withdraws from the study, the participant may request destruction of any samples taken and not tested, and the Investigator must document this in the site study records.

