8.1.4 Instructions for Dosing Regimen

Participants will self-administer study product at home, QD, and will record the time of application in a daily diary provided by the study site.

Application Instructions

Participants will be instructed to:

- Treat all lesions in the head and neck region, both newly appearing lesions and lesions that have improved or cleared during the study

Note: Participants may treat plaque PSO in other areas according to instructions provided in the USPI. No other treatment for scalp PSO is permitted during the study.

- Apply cream to dry, clean skin in an amount sufficient to completely cover each lesion with a thin layer
- Continue to lightly rub any residual cream visible on the disease-affected skin until it is no longer visible
- Wash hands after application, unless treating lesions on the hands or fingernails

Timing of Application

Participants will be instructed to:

- Maintain the approximate time of day for dosing at home throughout their full study participation
- Record the time of application in the daily diary
- Apply cream at least 30 minutes prior to bedtime if their chosen application time is in the evening
- Avoid swimming, bathing, showering, or strenuous activities for at least 2 hours after application

Missed Doses

A missed daily dose will be recorded as a protocol deviation.

Participants will be instructed that if a dose is missed, they should continue dosing the next day and should not apply more than QD to make up for the missed dose on the previous day.

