5.4. Statistical Hypotheses

Not applicable. Demographic and baseline characteristics, efficacy, safety, will be summarized descriptively. No inferential testing will be performed.

5.5. **Multiplicity Adjustment**

Not applicable

5.6. **Missing Data**

Every effort will be made to collect complete data at all visits.

All efficacy data will be summarized based on observed cases (OC).

Imputation of Missing Efficacy Data

In addition to the efficacy analysis based on OC, the primary and exploratory efficacy endpoints will also be summarized utilizing the last observation carried forward (LOCF) method to impute missing data . Baseline will not be used when applying LOCF and LOCF will be

implemented through Week 12 (i.e., Week 13 not included in LOCF). LOCF summaries will be considered supportive.

5.7. **Interim Analysis**

Not applicable

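### A target-lesion PGA scored after other psoriasis therapy or UV exposure still counts as a VTAMA response in the visible SAP, and no supportive analysis separates it

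*Protocol*

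**What the plan says.** **On-study therapy.** Protocol 5.2 item 7 lists prohibited medications with washout periods and adds: "If a participant requires any of these medications throughout the study period, he/she may be excluded from or discontinued from the study". Protocol 6.9 allows concomitant drugs on condition that the dose is not planned to change "and that the medication is not a prohibited medication as described in Section 5.2". Protocol 8.1.4 adds, in a note to the participant instructions: "No other treatment for scalp PSO is permitted during the study". Protocol 7.2 leaves removal for non-compliance to judgement: "A participant may be withdrawn at any time at the discretion of the Investigator for safety or compliance reasons".

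**UV.** This is a separate exclusion, 5.2 item 10. It covers exposure in the 4 weeks before Baseline and "plans to have such exposures during the study which could potentially impact the participant's PSO". No visible text says what follows if exposure happens on study.

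**Skin reactions.** Protocol 7.1.1 allows interruption of the product and remarks: "After cessation of exposure, dermatological reactions generally subside spontaneously or with topical treatments". Under 7.1.2 the product may then be resumed.

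**Analysis.** SAP 5.2 and 7 use all enrolled participants. SAP 5.6 summarises efficacy on observed cases, with LOCF as supportive. SAP 5.1 bases Kaplan-Meier on observed cases. SAP 5.3 uses nominal visits and windows early-termination and unscheduled assessments, with Week 12 opening at Day 72. SAP 6.2 counts and lists deviations, and SAP 6.6 tabulates and lists medications.

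**The concern.** The primary objective is the efficacy of VTAMA, and the study has a single open-label arm. If a participant's target lesion clears after another antipsoriatic drug or UV exposure, no comparator carries the same outside effect and nothing in the visible analysis sets the score apart. The response is then read as a VTAMA response, both in the Week 12 rate and in the time to onset. The confidence interval does not help, because it reflects sampling error and not wrong attribution. What is at stake is the size and meaning of a descriptive rate in about 30 people.

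**Working it through.** The plan states no power, alpha, effect size or expected response rate, so there is no figure to reproduce. The check has two parts.

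**1. Following such a score through the documents**

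- *Does use remove the participant?* Not necessarily. The 5.2 NOTE and 7.2 are both discretionary, and for UV no on-study consequence is visible.
- *Does use remove the score?* No visible rule does so. SAP 5.2, 5.6 and 7 take every observed PGA in all enrolled participants, and no per-protocol set is visible.
- *Does LOCF change it?* No. It fills missing values and leaves observed scores as they are.
- *Would discontinuation protect the endpoint?* Not fully. An early-termination PGA from Day 72 can fall in the Week 12 window (SAP 5.3), and LOCF can carry an earlier post-baseline score to Week 12 (SAP 5.6).
- *Does time to response treat it differently?* No visible censoring rule appears in SAP 5.1 or 7.2.
- *Is the use recorded?* Yes. Drugs are recorded with reason and dates (protocol 6.9) and listed (SAP 6.6), and deviations are listed (SAP 6.2). Neither output is linked to efficacy.

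**2. Size**

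Inputs: N = 30 (SAP 4); exact Clopper-Pearson 95% intervals (SAP 5.1). The starting counts x and the number affected k = 1 to 3 are assumptions.

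Overstatement = k/30, where k is the number of counted responders who would not have responded on VTAMA alone:

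- k = 1: 1/30 = 3.3 points
- k = 2: 2/30 = 6.7 points
- k = 3: 3/30 = 10.0 points

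With k = 3, the rate as observed is x/30. Counting the three as non-responders gives (x − 3)/30; setting them to missing gives (x − 3)/27.

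| Assumed x | As observed (95% CI) | Three as non-responders | Three set to missing |
|---|---|---|---|
| 12 | 40.0% (22.7–59.4) | 30.0% (14.7–49.4) | 33.3% (16.5–54.0) |
| 15 | 50.0% (31.3–68.7) | 40.0% (22.7–59.4) | 44.4% (25.5–64.7) |
| 18 | 60.0% (40.6–77.3) | 50.0% (31.3–68.7) | 55.6% (35.3–74.5) |
| 21 | 70.0% (50.6–85.3) | 60.0% (40.6–77.3) | 66.7% (46.0–83.5) |

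For scale, the interval at 15/30 is already 68.7 − 31.3 = 37.4 points wide. If fewer than 30 participants have a Week 12 PGA, each case weighs more; with 27 observed, 1/27 = 3.7 points.

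**The case against.** The strongest reply is that using every observed score in all enrolled participants is a legitimate treatment-policy approach, and that a descriptive Phase 4 study with so wide an interval does not need more. Drug use can be found in the listings and, with about 30 people, matched by hand to the PGA scores. This is fair as far as it goes, and it is why the observed-case analysis should remain primary. It does not supply a prespecified analysis, and matching after the results are known is weaker than a rule fixed beforehand.

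Several stronger readings are tempting, and the documents do not support them:

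- *The protocol tolerates other psoriasis drugs on the face and neck because 8.1.4 names only the scalp.* Section 6.9 bars the 5.2 medications on study, and that list is not limited by body site. The scalp note adds to this ban and does not narrow it.
- *The discretionary NOTE also governs UV.* It refers to the item 7 medications. UV is item 10.
- *Section 7.1.1 points to corticosteroid use on the target lesion.* It reports past experience, names no agent and no site, and does not say whether the 5.2 list still applies. It makes a route conceivable, not likely.
- *Every user inflates the rate.* A user who still fails, or who would have responded anyway, adds nothing.

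Redaction is also a real limit. Text is missing after the LOCF sentence (protocol 9.3.1, SAP 5.6), the Kaplan-Meier sentence in SAP 7.2 breaks off, and the content of SAP 7.3 and of the Schedule of Activities is not shown. A handling rule or a UV question could sit there.

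**Conclusion.** The point holds for the visible plan. Therapy listed in 5.2 is barred on study, but its use has only a discretionary consequence. On-study UV has none that can be seen. A PGA scored afterwards counts in both the primary and the secondary endpoint. The overstatement is 3.3 points at N = 30 for each counted responder who would not have responded on VTAMA alone, and 10 points for three. This rests on an assumed number of cases, since the documents give none; it may be zero. No hypothesis is tested, so the issue is what the rate can be attributed to, not type I error. A supportive analysis should be added; the primary analysis need not change.

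**What to change.** Keep the observed-case primary analysis and add one supportive analysis to SAP 7.2:

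1. Before database lock, flag each participant who, between first dose and the Week 12 PGA, used a 5.2-listed therapy capable of treating the target lesion, or had UV exposure of the type in item 10 where it is recorded. Limiting the flag in this way matters: the 5.2 list also holds drugs that may worsen psoriasis, and a medicated shampoo need not bear on a facial target lesion.
2. For the Week 12 rate, count flagged participants as non-responders.
3. For time to response, count only events that occur before such use, and state how flagged participants with no earlier event are censored.
4. Report the number flagged beside the primary rate. A count of zero would itself be useful.

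Separately, the sponsor should reconcile protocol 5.2 (NOTE), 5.2 item 10, 6.9, 7.1.1 and 8.1.4 on which other treatments are barred on study. No clinical rule is proposed here.

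The cost is SAP wording, one flag built from medication data already collected with reason and dates, and two supportive outputs. Sample size and visit schedule are unaffected. The downside is that the supportive rate can be lower, by 3.3 points per reclassified responder at N = 30, and may count as failures some participants who would have responded anyway. That is why it should stand beside the primary result and not replace it.
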